**Table 5-11 Clinically notable criteria for selected hematology tests**

Laboratory parameter	US or Other unit		SI unit	
	Lower bound	Upper bound	Lower bound	Upper bound
Notable value				
Hemoglobin	8(g/dL)	20 (g/dL)	80 (g/L)	200 (g/L)
Hematocrit	24%	60%	0.24 (v/v)	0.6 (v/v)
White blood cells	2 (x10  /uL)	35 (x10  /uL)	2 (x10  /L)	35 (x10  /L)
Platelets	50 (x10  /uL)	1000 (x10  /uL)	50 (x10  /L)	1000 (x10  /L)
Neutrophils	10 (x10  /uL)		10 (x10  /L)	

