4.5 Risks and benefits

The USM Follow up Investigator Notification (06-Dec-2022) was issued by Novartis to inform investigators that Novartis has decided to discontinue development of branaplam as a potential treatment for people with Huntington's disease. The decision followed a review of unblinded data from VIBRANT-HD indicating that the benefit:risk of

branaplam in Huntington's disease is not positive. This decision was endorsed by the independent Data Monitoring Committee (DMC) as well as the VIBRANT-HD Steering Committee (SC). Evaluation of risk for branaplam in patients with HD is based on preclinical data and the current clinical development experience in Type 1 SMA study in young children and healthy adult volunteers.

Table 4-2 summarizes the important potential risks from this experience.

Table 4-2 Summary of important risks

Class/Compound	Risk Classification	Risk Name	
Compound	Potential	Cell Cycle Effects	Bone marrow effects
			Gastrointestinal effects
			Nerve fiber degeneration
			Retinal atrophy
			Gonadal Effects: Testicular/Ovarian
			Reproductive toxicity: Pregnancy in Women of Child Bearing Potential
			Genotoxicity (aneuploidy*)
			Liver function effects
			Cardiovascular effects
			Renal toxicity
			DDI
-	Missing Information	Effects of Breastfeeding	
Class	None	None	

*Branaplam was not mutagenic in a bacterial mutagenicity (Ames) test. Branaplam is aneuploidic but not clastogenic. A neoplastic risk of branaplam as a consequence of the aneuploidic effect is considered unlikely but cannot be excluded.

Branaplam causes stabilization of tubulin polymerization, resulting in cell cycle arrest within the range of doses that are pharmacologically active. Based on animal studies this cell cycle arrest can potentially present in various organ systems such as gastrointestinal, bone marrow, nervous system, retina, reproductive effects, organs and liver toxicities. The hematologic effects can include various forms of cytopenias such as neutropenia, anemia and thrombocytopenia. Gastrointestinal effects can present as emesis, loose stools, or malabsorption.

Bone Marrow Effects

In the ongoing study in Type 1 SMA patients some events of cytopenias (neutropenia, anemia, and thrombocytopenia) were reported. However, these events were mild to moderate and reversible. Additionally, events of increased platelet counts were also reported which were also mild to moderate in severity and resolved spontaneously while on treatment.

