- Screening ECHO abnormalities per investigator's medical judgement including but not limited to left ventricular ejection fraction (LVEF) $<50\%$.
- Screening or baseline not within normal range Troponin or NTproBNP values.
- History or concomitant clinically significant cardiac arrhythmias (e.g., sustained ventricular tachycardia, atrial fibrillation, etc.), complete left bundle branch block, high-grade atrioventricular (AV) block (e.g., bifascicular block, Mobitz type II and third-degree AV block).
- History of familial long QT syndrome or known family history of Torsade de Pointes risks for TdP including uncorrected hypokalemia or hypomagnesemia, history of

clinically significant/symptomatic bradycardia and a family history of idiopathic sudden death.

- Resting QTcF ≥ 450 msec (male) or ≥ 460 msec (female) at pretreatment [screening or baseline] (as mean of triplicate ECGs), or inability to determine the QTcF interval.
- Use of agents known to prolong the QT interval or with a known or possible risk of Torsade de Pointes unless it can be permanently discontinued or replaced with a permitted medication (refer to [Table 6-2](#)).

15a. Uncontrolled hypertension (average 3 systolic blood pressure [SBP]readings) at screening >140 mmHg or average diastolic blood pressure [DBP] > 90 mmHg excluding values related to white coat syndrome (anxiety-related), per Investigator's judgement. Any clinically significant hematological abnormality as assessed by the Site Investigator at screening and/or laboratory evidence of any of the following:

- INR, PT, or activated partial thromboplastin time (APTT) that are not within normal ranges
- Hemoglobin <110 g/L (females) or <120 g/L (males)
- Platelets $\leq 100 \times 10^9$ /L
- Platelets count $>500 \times 10^9$ /L
- Neutrophil count $<1.5 \times 10^9$ /L
- Leukocytes $<3.0 \times 10^9$ /L

6 Treatment

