6.5.2 Dose modifications

For participants who do not tolerate the protocol-specified dosing schedule, dose interruptions are permissible, in order to allow participants to continue the study treatment.

Any changes in study treatment administration must be recorded on the Drug Administration Record eCRF.

If the administration of study treatment is temporarily interrupted for reasons other than toxicity, then treatment may be resumed at the same dose level and same dosing frequency.

If the study treatment is withheld due to toxicity, refer to Safety Monitoring [Section 10](#); scheduled visits and all assessments should continue to be performed (with the exception of the dosing of the withheld study drug), as described in the visit assessment schedule ([Table 8-2](#), [Table 8-3](#) and [Table 8-4](#)).

Beyond the DRF period and upon consultation with the Sponsor, the Investigator may consider to permanently discontinue a participant from the study in cases of extended interruptions and/or suspected non-compliance with study treatment (e.g. extended interruptions of study treatment not described in [Table 6-3](#) and in Safety Monitoring and Reporting [Section 10](#)).

All participants will be followed for safety until 30 days after the last dose of study treatment.

Deviations from mandatory dose interruptions are not allowed. Permanent study drug discontinuation is mandatory for specific events indicated in the [Table 6-3](#).

Table 6-3 Investigator Guidance for Dose interruption/discontinuation, follow-up and re-initiation of study treatment for select Adverse Events

Investigations (Hematologic)	
Neutropenia (absolute neutrophil count (ANC))	
Mild (ANC < lower limit of normal (LLN) - 1500/mm ³)	Recommendation: May maintain dose
Moderate (ANC < 1500 - 1000/mm ³)	Recommendation: May maintain dose
Severe (ANC < 1000 - 500/mm ³)	
Recommendation: Hold the study drug until resolved to mild or moderate, then maintain dose or consider every other week dosing after discussing with Sponsor
 
Mandatory: If ANC < 500 mm³, hold the study drug until resolved to mild or moderate; if resuming dose use clinical judgement.

Febrile neutropenia (ANC < 1.0 x 10 ⁹ /L, fever ≥ 38.5°C)	Recommendation: Hold the study drug and consider permanent discontinuation
Thrombocytopenia	
Mild (platelets (PLT) < LLN - 75,000/mm ³)	Recommendation: May maintain dose
Moderate (PLT < 75,000 - 50,000/mm ³)	Recommendation: May maintain dose

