Severe (PLT < 50,000 - 25,000/mm ³)	
Recommendation: Hold the study drug until resolved to mild;
 
 • If resolved in ≤ 7 days, then maintain dose • If not resolved in ≤ 7 days, then may consider permanent discontinuation at • Investigator's discretion or if resolved > 7 days to mild consider every other week dosing after discussing with Novartis 
Mandatory: If platelets <25,000/mm³, Hold the study drug and permanently discontinue or if resolved > 7 days to mild consider every other week dosing after discussing with Novartis

Thrombocytosis	
Mild (PLT > 500,000-700,000/mm ³)	Recommendation: May maintain dose (monitor prior to next dose)
Moderate (PLT >700,000 – 900,000/mm ³)	Recommendation: May hold dose until resolved to mild (monitor prior to next dose)

	
 • If resolved in ≤ 7 days, then maintain dose • If not resolved in ≤ 7 days, hold dose until resolved to mild, may consider permanent discontinuation at Investigator's discretion or if resolved > 7 days to mild consider every other week dosing after discussion with Novartis
Severe (PLT $> 900,000/\text{mm}^3$)	
Recommendation: Hold the study drug until resolved to mild (monitor prior to next dose)
 
 • If resolved in ≤ 7 days, then maintain dose • If not resolved in ≤ 7 days, then may consider permanent discontinuation at Investigator's discretion or if resolved > 7 days to mild consider every other week dosing after discussion with Novartis 
Mandatory: If platelets $> 1,000,000/\text{mm}^3$, permanently discontinue study drug. Manage per standard of care.

Cardiovascular disorders	
Hypertension	
(Systolic BP ≥ 160 mmHg or diastolic BP ≥ 100 mmHg)	
Recommendation: Hold the study drug, treat per standard of care until resolved
 
Mandatory: In case of life threatening consequences of hypertension e.g. malignant hypertension, transient or permanent neurologic deficit, hypertensive crisis, permanently discontinue study drug immediately. Manage per standard of care

Cardiac Echocardiogram Left Ventricular Ejection Fraction (LVEF) $< 50\%$ and/or Reductions in LVEF $\geq 10\%$ units and/or GLS $\geq 15\%$ units change from baseline	
Recommendation: Hold the study drug and continuing study treatment should be done in consultation with a cardiologist. Manage per standard of care.

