### **Summary tables**

- Absolute values and change from baseline will be summarized for continuous laboratory parameters by visit.
- For selected laboratory tests, the number and percentage of participants with newly occurring or worsening laboratory/liver enzyme abnormalities meeting the clinically notable criteria at any time post baseline will be summarized. Clinically notable criteria are defined in [Appendix 5.5](#).

For a participant to meet the criterion of a newly occurring clinically notable value, the participant needs to have a baseline value that is not clinically notable for that parameter. For a participant to meet the criterion of a worsening clinically notable value, the participant needs to have a baseline value that is clinically notable and also have a worse post-baseline value. For participants with missing baseline value, any post-baseline notable value will be considered as newly occurring.

For each participant, all applicable post-baseline values (including unscheduled or unplanned visits) will be checked against the respective criteria. If at least one of the results, for a particular parameter, exceeds the criteria, the participant will be considered as clinically notable abnormal for that parameter. A participant can be counted in both low and high categories. If multiple

abnormality occurrences exist for the same lab parameter, the worst case within a lab parameter will be used to categorize the abnormality.

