## Listings

- Laboratory data of participants with at least one clinically notable value will be listed.

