## **5.4 Visit windows**

In general, if two consecutive visits  $V_t$  and  $V_s$  are  $x$  days apart, the upper limit of the visit window for  $V_t$  will be  $V_t+x/2$  and the lower limit for the visit  $V_s$  will be  $V_s-x/2 + 1$  (if  $x$  is even). The algorithm needs to ensure that visit windows are not overlapping and that there are no gaps, such that each assessment can be uniquely allocated to one visit window.

Both scheduled and unscheduled assessments will be considered.

In case of competing assessments within a visit window:

- For efficacy parameters: the assessment value closest to the scheduled visit day will be used. In case of equal distances, the earliest assessment value will be used.
- For safety parameters: the worst assessment value within the visit window will be used (see [Section 5.4](#)). If more than one assessments are equally worst, the one closer to visit window will be used.

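### SAP Table 5-11 prints a neutrophil lower notable limit of 10 x 10^9/L, which is incompatible with its own white-cell lower limit of 2 and makes the neutrophil abnormality count and listing uninformative

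*SAP*

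**What the plan says.** SAP Section 5.5, Table 5-11 ("Clinically notable criteria for selected hematology tests") has lower-bound and upper-bound columns in two unit systems. White cells have a lower limit of 2 and an upper limit of 35 x 10^9/L. Platelets have 50 and 1000. Neutrophils have 10 in both lower-bound columns and nothing in the upper-bound columns. The table prints no inequality signs, so the column alone gives the direction.

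SAP Section 2.7.3 applies these limits to all post-baseline values, unscheduled ones included, and counts participants whose abnormality is newly occurring or worsening. For worsening, "the participant needs to have a baseline value that is clinically notable and also have a worse post-baseline value". The listing rule is wider: "Laboratory data of participants with at least one clinically notable value will be listed".

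Protocol Section 5.2 (item 15a) excludes "Neutrophil count $<1.5 \times 10^9$ /L". Protocol Table 6-3 grades neutropenia at 1500, 1000 and 500 per mm3; its severe grade begins "Severe (ANC < 1000 - 500/mm". Protocol Section 4.5 names the risk: "The hematologic effects can include various forms of cytopenias such as neutropenia, anemia and thrombocytopenia".

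**The concern.** A lower limit of 10 x 10^9/L would class almost every participant as having a notably low neutrophil count before the first dose. The worsening rule would then apply to nearly everyone, and it needs only one later value below baseline, however small the drop. The count would measure visit-to-visit fluctuation, in much the same way in both arms.

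Safety and tolerability is one of the two primary objectives, and neutropenia is a named risk. The notable-abnormality table is where a reader would look for the number of participants with a low neutrophil count. As printed, that line could not separate drug-related neutropenia from ordinary variation.

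**Working it through.** **1. Units.** 10 x 10^3 per uL x 10^6 uL per L = 10 x 10^9/L. The two printed values agree, so this is not a unit slip.

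**2. Against the white-cell row.** The neutrophil count cannot exceed the white count. If 2 <= white cells < 10, then neutrophils < 10. Such a participant is inside the white-cell limits and below the neutrophil limit in every case. The neutrophil limit is 10/2 = 5 times the white-cell limit.

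**3. Against the protocol** (1000/mm3 = 1.0 x 10^9/L).
- Entry limit and mild/moderate boundary 1.5: 10/1.5 = 6.7 times.
- Moderate/severe boundary 1.0: 10/1.0 = 10 times.
- Lowest boundary 0.5: 10/0.5 = 20 times.

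The platelet row does line up with Table 6-3. Its lower limit of 50 x 10^9/L is the 50,000/mm3 at which "Severe (PLT < 50,000 - 25,000/mm" starts, and its upper limit of 1000 is the 1,000,000/mm3 in the thrombocytosis rule.

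**4. Chance flag rate under SAP Section 2.7.3.** Neither document gives a neutrophil distribution or a flag rate, so this is illustration only. Assume nearly all baselines are below 10, visits are exchangeable with baseline, and there is no drug effect. A participant is flagged if any of k post-baseline values is below baseline. Baseline is the lowest of k + 1 exchangeable values with probability 1/(k + 1), so P(flagged) = k/(k + 1).

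| Period | k | k/(k + 1) |
|---|---|---|
| Through Week 17 (Weeks 2, 3, 5, 9, 13, 17) | 6 | 6/7 = 85.7% |
| Through Week 33 (adding 21, 25, 29, 33) | 10 | 10/11 = 90.9% |
| Through Week 69, if the Week 53 and 69 samples are drawn | 12 | 12/13 = 92.3% |

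The k = 10 row assumes hematology at Weeks 21, 25 and 29. The k = 12 row can apply only to branaplam participants, because placebo participants may leave at Week 33. At Weeks 53 and 69, protocol Table 8-5 recommends laboratory tests only where an adverse event requires them. Unscheduled samples would raise all three rates.

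**5. Simulation check.** 400,000 participants; lognormal counts with assumed median 3.5 to 4.5 x 10^9/L, between-person log-SD 0.3 and within-person log-SD 0.2; baseline at least 1.5; values rounded to 0.1 or 0.01.
- Baseline below 10: 98.6% to 99.8%.
- Flagged: 84% to 86% (k = 6), 90% to 91% (k = 10), 91% to 93% (k = 12).
- Any post-baseline value below 10, which is enough for the listing: at least 99.9%.

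For scale, the same model at the protocol's own boundaries gives 0.4% to 2.9% (k = 6) and 0.7% to 4.0% (k = 10) at 1.5, at most 0.1% at 1.0, and 0.0% at 0.5.

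**6. Planned arm.** For 25 participants at 4:1 and k = 6, chance alone would flag about 20 x 6/7 = 17.1 on active and 5 x 6/7 = 4.3 on placebo.

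**The case against.** **The protocol values do not bind the SAP.** A reader might infer a direct contradiction with the protocol. The SAP does not say that notable limits must equal entry or dosing boundaries, and other rows differ: hemoglobin 80 against entry limits of 110 and 120 g/L, white cells 2 against 3.0, platelets 50 against 100. This stands. The protocol figures show implausibility; the incompatibility lies within Table 5-11. Those other lower limits do all fall below the entry limit, so they are more extreme than it. Only the neutrophil limit lies above it.

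**The direction may be misread.** Table 5-13, in the same section, has fewer cells per row than column headings in the available text, so a shifted column cannot be excluded. Against that, Table 5-12 keeps albumin (lower only) and GGT (upper only) in the expected columns, and the neutrophil blanks fall symmetrically in both unit systems. A misplaced upper limit or a lost decimal remains possible. If 10 was meant as an upper limit, Table 5-11 has no low-neutrophil criterion. The row needs correcting on either reading.

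**The effect is narrow and visible.** Dosing has ended, treatment is unblinded and the analysis is descriptive. By-visit values and changes, box-plots and adverse event tables can still show neutropenia, and a line that flags nearly everyone in both arms would be noticed. This stands and limits the severity.

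**A wider reach might be inferred.** SAP Section 5.4 says that for safety parameters "the worst assessment value within the visit window will be used", so a reader might suppose that the faulty direction also alters the by-visit summaries. Section 5.4 does not define worst by Table 5-11, so the documents do not support that step.

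**Conclusion.** The point holds for the neutrophil row only. The printed lower limit cannot stand beside the white-cell limit, and the notable-abnormality count and listing for neutrophils would be uninformative if it were applied.

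That conclusion needs only that nearly all baselines lie below 10. The percentages need more: exchangeable visits, no drug effect and an assumed number of samples. A reader might take a single figure near 85% as a consequence of the plan. Neither document states it, and it fits only the six visits through Week 17. SAP Section 2.1 specifies one cumulative period, for which the range in the working (84% to 93%) is the fairer statement. Nor do the documents show that neutropenia would go undetected, since the other safety outputs remain. It should be fixed before reporting, but it does not threaten the safety analysis as a whole.

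**What to change.** Before the final tables are run:
- Check the neutrophil row against the source for Table 5-11 and state its direction explicitly.
- If 10 was intended as an upper limit, move it to the upper-bound columns.
- Set a low-neutrophil reporting limit reconciled with the white-cell row and the neutrophil boundaries already in the protocol, and record the reason for the choice.
- Rerun the notable-abnormality table and the associated listing.

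The cost is one SAP table row and two outputs, with no new data. The latest SAP version is dated 26-Oct-2023, before last participant last visit, so the row could still be corrected ahead of final reporting. This is a reporting threshold only; it changes no dosing rule in protocol Table 6-3.

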**Table 5-12 Clinically notable criteria for selected chemistry tests**

Laboratory parameter	US or Other unit		SI unit	
	Lower bound	Upper bound	Lower bound	Upper bound
Notable value				
Sodium	120 (mmol/L)	160 (mmol/L)	120 (mmol/L)	160 (mmol/L)
Potassium	3 (mmol/L)	6 (mmol/L)	3 (mmol/L)	6 (mmol/L)
Magnesium	1 (mg/dL)	6.1(mg/dL)	0.4 (mmol/L)	2.5 (mmol/L)
Albumin	25 (g/L)		25 (g/L)	
Gamma-glutamyl-transferase (GGT)		3 X ULN		3 X ULN
estimated Glomerular filtration rate (eGFR)	<=30 (mL/min)		<=30 (mL/min)	
Lipase		1.5 x ULN		1.5 x ULN
Amylase		1.5 x ULN		1.5 x ULN
Notable relative change from baseline				
Creatinine*		>50%		>50%
* Baseline Creatinine is calculated as the average of screening and baseline (if either one is missing, the non-missing one will be used as baseline, if multiple screening assessments is available, average screening assessments first and then average with baseline)				

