Testicular atrophy	
Recommendation: If FSH level doubles from baseline and absolute value is above 5 IU/L then consult endocrinologist. Use clinical judgment for continuation of study drug; discuss with participant.

Neurologic Findings	
Neurologic Findings suggestive of peripheral neuropathy	
Recommendation: Consider withholding study drug under the following conditions:
 
 • Any clinically significant neurologic finding on the comprehensive neurologic exam with or without a positive response on neurology questionnaire. The following should be actioned: 
 • Perform Compound Motor Action Potential (CMAP)/ Sensory Nerve Action Potential (SNAP) 
Follow-up as per Investigators judgement
 
 • In case of inconclusive CMAP or SNAP results, Investigator may use clinical judgement regarding discontinuation or withholding study drug 
Mandatory: Discontinue study drug immediately and permanently under the following conditions:
 
 • Any clinically significant abnormality in the comprehensive neurology exam and CMAP or SNAP. Continue to follow patient (to resolution). Refer to Section 8.4.4
Ophthalmological Findings	-
Retinal Atrophy	
Recommendation: Any new retinal findings from baseline which in the opinion of the Investigator is related to the study drug, discontinue the study drug permanently. Manage as per standard of care.

Refer to [Appendix 1 \(Table 16-1 and Table 16-2\)](#) for guidance on hepatic events and [Appendix 2 \(Table 16-3 and Table 16-4\)](#) for guidance on renal events.

This guidance does not provide an exhaustive list of AEs and Investigators should use their clinical judgement when assessing dose interruption for those AEs not mentioned in the table.

Participants whose study treatment is temporarily interrupted or permanently discontinued due to an AE or abnormal laboratory value must be followed until resolution or stabilization of the event, whichever comes first, including all study assessments appropriate to monitor the event as described in this section. In the event study treatment has been temporarily interrupted (> 7 days) due to an AE or laboratory abnormality not listed in [Table 6-3](#), study treatment may be re-challenged to an every other week dosing after discussing with the Novartis.

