8.4.5.4 Reproductive system/fertility assessments

Fertility hormones

The cell cycle arrest properties of branaplam may also have an effect on male and female fertility. The clinical Investigator will discuss fertility preservation measures (such as sperm banking, egg harvesting) with the patients during Screening. In order to monitor the potential effects of branaplam on testicular function, specifically spermatogenesis, FSH levels will be

[figure not shown]
obtained at baseline and then at regular intervals during the course of the study. If FSH levels double from the patient's BL **and** is above 5 IU/mL consultation with an endocrinologist is recommended.

[figure not shown]

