10.2.2 Renal safety monitoring

The following two categories of abnormal renal laboratory values have to be considered during the course of the study:

- Serum creatinine increase $\geq 25\%$ compared to baseline during normal hydration status
- Urine protein-creatinine ratio (PCR) ≥ 1 g/g or ≥ 113 mg/mmol, OR new onset dipstick proteinuria $\geq 3+$ OR new onset dipstick hematuria $\geq 3+$ (after excluding menstruation, urinary tract infection (UTI), extreme exercise, or trauma)

Abnormal renal event findings must be confirmed within 24-48 hours after the first assessment.

Every renal laboratory trigger or renal event as defined in [Table 10-2](#) should be followed up by the Investigator or designated personnel at the trial site as summarized in [Section 16.2](#).

Since this is an early phase study baseline serum creatinine is determined as the mean of two serum creatinine measurements (e.g. at screening and pretreatment).

Table 10-2 Renal Events and Definition and Diagnosis

A renal event is defined as the presence of any of the following	Confirm Finding
GFR Event Serum creatinine increase \geq 25% versus baseline Note: Dependent on NORMAL hydration status, see the list below	Confirm assessment 24 - 48 h after first assessment
Urine Event Protein-creatinine ratio $>$ or $=$ 1 g/g Cr or \geq 113 mg/mmol New onset dipstick proteinuria \geq 3+ New onset dipstick hematuria \geq 3+*	
*Exclude menstruation, urinary tract infection (UTI), extreme exercise or trauma, and bleeding from the distal urinary tract/bladder	

When assessing (Drug Induced Nephrotoxicity (DIN) renal events, also consider other causes of renal events and/or altered serum creatinine and BUN:

- Hypovolemia
- Major operations
- Severe infections and sepsis
- Co-medications affecting creatinine secretion (e.g., trimethoprim, cimetidine)
- Change of antihypertensive treatment regimens
- Acute or worsening heart failure
- Rhabdomyolysis (monitor for increase in CPK)

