16.2 Appendix 2: Specific Renal Alert Criteria and Actions and Event Follow-up

Table 16-3 Specific Renal Alert Criteria and Actions

Renal Event	Actions
Confirmed serum creatinine increase 25 – 49%	
 Consider causes and possible interventions Follow up within 2-5 days
Serum creatinine increase 50 % ⁺	
 Consider causes and possible interventions Repeat assessment within 24-48h if possible Consider drug interruption or discontinuation unless other causes are diagnosed and corrected Consider participant hospitalization and specialized treatment
New onset dipstick proteinuria $\geq 3^+$ OR Protein-creatinine ratio (PCR) $\geq 1\text{g/g Cr}$ (or $\geq 113\text{ mg/mmol}$ equivalent as converted by the measuring laboratory)	
 Consider causes and possible interventions Assess serum albumin & serum total protein Repeat assessment to confirm Consider drug interruption or discontinuation unless other causes are diagnosed and corrected
New onset hematuria $\geq 3^+$ on urine dipstick	
 Repeat assessment to confirm Distinguish hemoglobinuria from hematuria Urine sediment microscopy Assess sCr Exclude UTI, trauma, bleeding from the distal urinary tract/bladder, menstruation and extreme exercise Consider bleeding disorder

⁺ Corresponds to KDIGO criteria for Acute Kidney Injury

Additional specialized assessments are available to assess renal function or renal pathology. (Note: In exceptional cases, when a nephrologist considers a renal biopsy, it is recommended to make slide specimen available for evaluation by the RSG to potentially identify project-wide patterns of nephrotoxicity.)

Whenever a renal event is identified, a detailed participant history and examination are indicated to identify and potentially eliminate risk factors that may have initiated or contributed to the event:

- Blood pressure assessment (after 5-minute rest, with an appropriate cuff size)
- Signs and symptoms like fever, headache, shortness of breath, back or abdominal pain, dysuria or hematuria, dependent or periorbital edema
- Changes in blood pressure, body weight, fluid intake, voiding pattern, or urine output
- Concomitant events or procedures such as trauma, surgical procedures, cardiac or hepatic failure, contrast media or other known nephrotoxin administration, or other diseases or causes, e.g., dehydration due to delirium, tumor lysis

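### SAP Table 5-12 leaves creatinine rises of 25% to 50% out of the notable-value count, and Table 5-15 cannot identify the protocol's ALT/AST-with-INR liver event

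*SAP*

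**What the plan says.** **Renal, protocol.** Section 10.2.2 introduces Table 10-2 with "A renal event is defined as the presence of any of the following". The GFR entry is a serum creatinine increase of 25% or more versus baseline, under normal hydration, confirmed 24–48 hours later. On the reference value it says: "Since this is an early phase study baseline serum creatinine is determined as the mean of two serum creatinine measurements". Table 16-3 (section 16.2) has two creatinine rows with different actions, beginning "Confirmed serum creatinine increase 25 – 49" and "Serum creatinine increase 50" (both percentages). The second is footnoted as corresponding to KDIGO acute kidney injury.

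**Renal, SAP.** Table 5-12 has one creatinine row, a relative change above 50%, with the footnote "Baseline Creatinine is calculated as the average of screening and baseline". Table 5-13 carries the protocol's urine criteria: dipstick proteinuria, dipstick hematuria and protein-creatinine ratio.

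**Liver.** Protocol Table 16-1 lists ALT or AST >3×ULN with INR >1.5 as a liver event, and Table 16-2 gives it its own row of actions. SAP Table 5-15 has rows for ALT/AST, ALP, bilirubin and their combinations, including Hy's law, but none involving INR.

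**Use of the criteria.** SAP 2.7.3 counts participants with newly occurring or worsening notable values and restricts the listing: "Laboratory data of participants with at least one clinically notable value will be listed". Protocol 12.5.2 leaves the notable criteria to the SAP. SAP section 4, on changes to protocol-specified analyses, only points back to the preceding text.

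**The concern.** Safety and tolerability is one of the two primary objectives. Renal toxicity and liver function effects are named potential risks in protocol Table 4-2. Dosing ended for safety reasons, so the descriptive safety tables are the main product of the abbreviated report. A reader of that report will expect its renal and liver rows to line up with the events the protocol told sites to detect.

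For creatinine they do not, and the mismatch looks unintended. The SAP took over the protocol's averaged baseline and its urine criteria, but not the 25% threshold that belongs with them. The report could show no notable creatinine values while participants had met the protocol's own GFR definition. For the INR combination the participants appear in a broader row, but the more specific event cannot be read from it.

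**Working it through.** No sample size, power or event rate is involved. The check codes the two sets of rules and runs them on illustrative values, which are assumptions and not trial data.

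**1. Creatinine.** Baseline B = (screening + baseline)/2. Protocol threshold: value ≥ 1.25 × B. SAP threshold: value > 1.50 × B.

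| Rise over B | Protocol GFR event (if confirmed, normal hydration) | SAP notable |
|---|---|---|
| 24.9% | no | no |
| 25% | yes | no |
| 30% | yes | no |
| 49% | yes | no |
| 50% | yes | no |
| 50.1% | yes | yes |

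The documents give no typical baseline, so I assume three (µmol/L):

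- B = 60: 1.25 × 60 = 75 and 1.50 × 60 = 90, so 75 to 90 is missed.
- B = (78 + 82)/2 = 80: 1.25 × 80 = 100 and 1.50 × 80 = 120, so 100 to 120 is missed.
- B = 100: 1.25 × 100 = 125 and 1.50 × 100 = 150, so 125 to 150 is missed.

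The missed band is always 0.25 × B wide.

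**2. Whether another output recovers the count.**

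- The listing includes a participant only if some value is notable, so a 40% creatinine rise alone does not bring anyone into it.
- Table 5-12's eGFR row (30 mL/min or below) helps only where eGFR also falls that low.
- By-visit means and box plots do not give the number of participants at or above 25%. Cohort 1 was planned at about 25 participants randomized 4:1, so about 25 × 4/5 = 20 on active drug. One 40% rise moves their mean percentage change by 40/20 = 2 points.
- Adverse event tables include it only if the abnormality caused signs or symptoms, was judged clinically significant or needed therapy (protocol 10.1.1). The 25–49% row of Table 16-3 asks for causes, interventions and follow-up, not an adverse event record.

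**3. Liver.** Take ALT 4×ULN with normal bilirubin and ALP, and no symptoms.

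| INR | Protocol Table 16-1 | SAP Table 5-15 |
|---|---|---|
| 1.6 | liver event | ALT/AST >3×ULN |
| 1.0 | laboratory trigger only | ALT/AST >3×ULN |

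Both participants are counted, in the same rows. The other events in Table 16-1 defined only by ALT, AST, ALP or bilirubin thresholds each have a row in Table 5-15.

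**4. FSH, checked because Table 5-13 has two rows.** The protocol rule is doubling and a value above 5. A change from 2.4 to 5.5 meets it (5.5 ≥ 4.8) and meets the SAP's combined row. A change from 4 to 6 does not meet it (6 < 8), and meets only the SAP's stand-alone >5 row. In all seven cases tried, the combined row agreed with the protocol rule.

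The protocol's limit is stated two ways. Table 6-3 says "If FSH level doubles from baseline and absolute value is above 5 IU/L then consult endocrinologist", while section 8.4.5.4 says "is above 5 IU/mL consultation with an endocrinologist is recommended". Since 5 IU/mL = 5000 IU/L, these differ 1000-fold.

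**The case against.** The strongest reply is that Table 10-2 and Table 16-3 are site monitoring and action rules, that protocol 12.5.2 hands the notable criteria to the SAP, and that a cut near 50% matches the tier the protocol ties to acute kidney injury. Creatinine change is still summarized by visit, and clinically significant abnormalities are recorded as adverse events. The protocol event also requires normal hydration, which a laboratory-only row cannot apply.

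Much of this stands. A reader might infer that the SAP breaches the protocol. It does not, because the choice was delegated. What remains is an unexplained difference, with no output that gives the number at or above 25%. The hydration condition limits what the new row can claim but does not justify having none.

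A reader might also infer that renal and liver events in general go uncounted. The documents do not support that. The urine criteria match the protocol. Participants with raised ALT/AST and INR are counted under ALT/AST >3×ULN and their laboratory data are listed, INR is summarized with the coagulation group, and protocol Table 16-2 requires an adverse event record. They are unidentified as that event, not missing.

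Lastly, a reader might infer that FSH abnormalities are over-counted. Table 5-13 holds the protocol's combined rule as its own row, so that count is not inflated. The stand-alone row is a broader, separate flag, and keeping it is a matter of preference.

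**Conclusion.** The creatinine point holds: rises from 25% to 50% inclusive meet the protocol's numerical GFR criterion but trigger no SAP notable flag, and no reason is given. How many participants this affects cannot be known from the documents. The µmol/L bands rest on assumed baselines; the 25% to 50% gap does not.

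The liver point holds in a narrower sense: one protocol-defined event cannot be identified in Table 5-15, although its participants are counted there.

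Both are reporting gaps in descriptive tables and no inferential result depends on them. They are worth closing because safety is the report's main content and the change is cheap. The FSH unit conflict is a separate inconsistency within the protocol.

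**What to change.** - **Table 5-12:** add a row for a creatinine increase of ≥25% from baseline, shown as any occurrence and as confirmed where a repeat exists. Footnote that laboratory data alone cannot apply the protocol's normal-hydration condition. Change the existing row from >50% to ≥50% so that it meets the Table 16-3 tier.
- **Table 5-15:** add ALT or AST >3×ULN and INR >1.5, using the existing 3-day window for criteria with several parameters.
- If either addition is declined, state the reason in SAP section 4.
- **Protocol:** reconcile Table 6-3 and section 8.4.5.4 on the FSH unit.

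The cost is SAP wording and a few rows from central laboratory data already collected. The downside is that more participants will appear in the creatinine table, because 25% is a sensitive limit; the confirmed row helps the reader weigh them. SAP 2.7.3 reports central laboratory values only, so a repeat done locally would not count as confirmation. The post-USM schedule (protocol Table 8-5) lists no coagulation panel, so the INR row would rest on earlier scheduled samples and any unscheduled ones.
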